6.8 Sample Size Determination - Neuroimaging Sub-Study

We plan to test hypotheses at a global 5% Type I error (alpha) for each family of hypotheses, and have chosen a completed sample ($N=60$) that will achieve at least 80% power using 2-sided tests. Our analysis of power was based on “effect size” (standardized difference). Effect sizes were calculated from our own preliminary data, from published data summaries, and from published estimates of effects (e.g., t statistics, coefficients, p-values) using validated summary methods. We have several hypotheses and more than one outcome measure for some (e.g., different brain regions). We will control error in a family-wise manner, adjusting alpha (Bonferroni Aims 1 and 2, Hochberg step-up procedure for Aim 3) for the number of tests within each hypothesis family. Bonferroni corrections will also be adjusted for the correlations among multiple outcomes.

Aim 1 includes 2 hypotheses (**H1a&b**) regarding treatment effects on neural responses including 5 ROIs responding to food-related tasks. We test at $p<0.02$ because of the high correlation among ROIs within subjects ($\rho=0.54$). Estimates of effect size from our center data ($d=0.36$) indicate that we have 80% power to detect the effects. Aim 1 also tests hypothesis **H1c** for cessation effects. At the Bonferroni corrected threshold of $p=0.0167$, we have 80% power to detect small to medium effect sizes ($d=0.37$).

Aim 2 (H2a&b) essentially tests for mediation. The hypothesis that cessation increases food intake will be tested at 0.05, with power for effect sizes $\sim d=0.32$ [9, 58]. For Aim 2b (ROIs predicting food intake), we expect a weaker correlation than H1a ($\rho=0.4$), and our adjusted threshold for significance is $p<0.01$. Expected effect sizes are approximately 0.5, and we expect 96% power to detect the effects.

Aim 3 begins with the model in Aim 2b above, and tests interacting effects of working memory-related BOLD signal and food reinforcement (or food cue reactivity) on food intake. We will reduce the complexity of this analysis by using difference scores (pre minus post) to model a 2-

CONFIDENTIAL

This material is the property of the University of Pennsylvania. Do not disclose or use except as authorized in writing by the study sponsor

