Aim 1: Identify effects of BAS+ (vs SC) treatment on food related neural activity and behavior: These comparisons are all between subject, and will be analyzed using mixed models regression (xtmixed, StataCorp, Texas). The model predictors will include a binary indicator for group (BAS+ vs. SC). The hypothesis will be tested using the z-score corresponding to the main effect of group. Covariates can be included in the model to control error (sex, BMI, nicotine dependence, age, weight concerns), although we do not expect to make large gains for adding subject-level controlling variables in a mixed model.

Aim 2: Evaluate the relative contribution of these neural processes to post-cessation caloric intake: Our outcome variable is average daily calories based on food recalls. The first comparison (pre vs. post-treatment) is within-subject, and will be analyzed using mixed models regression with subject specific random effects. As before, we include a binary predictor for condition, a categorical indicator for serial day, and we will test using the z-score corresponding to condition. For testing candidate mediators, we will again model calories using mixed models, entering variables as time-varying (condition varying) predictors, along with subject specific random effects. Finally, we will build the larger model, looking for confounding that represents potential mediation. For this purpose, we will use regression-based multi-equation path models. Path Analysis partitions a directly measured bivariate relationship, for example, between abstinence and calories ingested, into direct and indirect causal paths, to tease apart the important components mediating the response. We will deem that mediation has occurred when a relationship between abstinence and food intake accounted in full, or in part, by one or more of the intervening variables (BOLD signal change or subjective responses in cessation vs. smoking). We will assess the strength of the indirect effects through confidence intervals, evaluate the proportion mediated (i.e., partial or complete mediation), and determine significance with Delta method standard errors. To assess the level of mediation for a pathway, we will estimate the ratio of the indirect effect to the total effect (i.e., effect proportion mediated $\beta_{\text{indirect}}/\beta_{\text{total}}$).

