Aim 3: Test whether cessation-induced working memory deficits moderate the relationship between neural responses to food cues and reinforcement and food intake: This implies a 3-way interaction for a repeated measures analysis (e.g. cessation condition by food reinforcement by working memory on food intake). We will reduce the complexity and eliminate the repeated measures by conducting the analysis using difference scores (pre vs post), and will use multiple linear regression to analyze the differences in food intake. We will model the brain responses to cue reactivity and to food reinforcement separately. The models will contain a term for the difference in BOLD signal, and we will introduce a candidate moderator.

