6.12 Statistical Methods - Microbiome Sub-Study

For **Aim 1, H1a**, the abundance of bacterial taxa will be analyzed at a community level using pairwise distance between samples, and visualized with Principal Coordinates Analysis. That pairwise distance will be the basis for the omnibus tests in all three aims. Prior to the testing of individual taxa, we will conduct a longitudinal MANOVA (Multivariate ANOVA) based on the profile of relative abundances of the gut taxa of interest. P-values from multiple testing procedures will be corrected to control for a specified false discovery rate using the Hochberg method. For **H1b**, we will repeat the omnibus MANOVA test as in H1a using the absolute levels of metabolites, and follow with tests on individual metabolites should the overall test prove significant. Smoking behavior (smoking rate) will be included in the statistical models for Aim 1 as a covariate, because not all participants will have maintained smoking abstinence from TQD through EOT. **Aim 2** will evaluate the impact of post-cessation changes (pre-post changes) in the gut microbiome on dietary intake (kcals, continuous outcome) and smoking cessation (point-prevalence, binary outcome). We will use generalized linear models fitted using Generalized Estimating Equations. We will specify the logistic model for the binary abstinence outcome, and

CONFIDENTIAL

This material is the property of the University of Pennsylvania. Do not disclose or use except as authorized in writing by the study sponsor

Gaussian dietary intake outcome. We will begin the analysis with the effect of the omnibus measure (pre-post distance). Should that prove significant, we will continue on to specific taxa and metabolites. **Aim 3** will explore whether treatment modifies the effect of gut microbiome changes on dietary intake and smoking cessation. We will enter interaction terms (e.g., treatment x microbiome changes) to the models generated for Aim 2. The interactions will be retained if the z-score is significant ($p<0.05$).

7 Risks / Benefits

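### Neuroimaging Aim 1 tests a between-subject group effect with a normal z-score at N of about 50 to 60, so a nominal 0.02 is about 0.024; microbiome Aim 3 has a similar, conditional gap (minor)

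*Combined protocol and SAP*

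**What the plan says.** Neuroimaging Aim 1 (section 6.11): "These comparisons are all between subject, and will be analyzed using mixed models regression (xtmixed, StataCorp, Texas"). The test is then fixed: "The hypothesis will be tested using the z-score corresponding to the main effect of group". Covariates are optional: "Covariates can be included in the model to control error (sex, BMI, nicotine dependence, age, weight concerns"), and the plan does not expect much gain from them. It does not say whether the fit is ML or REML, and it gives no degrees-of-freedom method.

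Thresholds (section 6.8): "We plan to test hypotheses at a global 5% Type I error (alpha) for each family of hypotheses". H1a and H1b cover five regions of interest (ROIs) and are tested at 0.02, citing a between-ROI correlation of 0.54. H1c is tested at 0.0167. The completed sample is 60 in section 6.8 but about 50 in sections 3.2 and 4.3, with equal arms.

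Microbiome Aim 3 (section 6.12) adds treatment interactions to the Aim 2 GEE models, Gaussian for kcal and logistic for abstinence: "The interactions will be retained if the z-score is significant", at p<0.05. N is 60 (section 6.9). No GEE variance estimator is named for these models.

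Other sub-study tests differ. Neuroimaging Aim 2 is a within-subject comparison: "we will test using the z-score corresponding to condition". For neuroimaging Aim 3 the plan "will use multiple linear regression to analyze the differences in food intake". Microbiome Aim 1 uses a longitudinal MANOVA.

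**The concern.** A z reference treats the standard error as known. For a between-subject effect, the variance is estimated from as many independent units as there are participants, less the number of fitted coefficients. With 50 to 60 people, the statistic has visibly heavier tails than the normal. A maximum-likelihood variance is also too small, by the factor (N-p)/N, and an uncorrected GEE sandwich is typically too small at this size. Each pushes the true rejection rate above the written threshold and narrows the confidence intervals. At stake is whether the stated thresholds mean what they say. The parent trial's primary outcomes are not involved.

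**Working it through.** **The plan's own figures.** A correlation-adjusted Bonferroni for five ROIs at correlation 0.54 gives 1 - 0.95^(1/5^0.46) = 0.0242, or 0.05/5^0.46 = 0.0238. The plan uses 0.02, apparently this value rounded down. The 80% power quoted in 6.8 for d=0.36 at two-sided 0.02 does not reproduce at N=60. A one-sample normal calculation gives 67.8%, and a two-group comparison with 30 per arm gives 17.6%. That is a separate and larger matter.

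**Neuroimaging Aim 1.** In a balanced design the group test equals a regression on subject means. With p fixed coefficients (2 for intercept and group, 7 with the five covariates) and critical value z:

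- Unbiased (REML-type) variance: level = 2·P(t[N-p] > z)
- ML variance: level = 2·P(t[N-p] > z·√((N-p)/N))

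For 0.02, z = 2.326. Example for ML, N=50, p=2: 2.326 × √(48/50) = 2.279, and 2·P(t[48] > 2.279) = 0.0271.

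| N | p | df | 0.02, REML | 0.02, ML | 0.0167, REML | 0.0167, ML |
|---|---|---|---|---|---|---|
| 50 | 2 | 48 | 0.0243 | 0.0271 | 0.0207 | 0.0232 |
| 60 | 2 | 58 | 0.0235 | 0.0258 | 0.0200 | 0.0220 |
| 50 | 7 | 43 | 0.0248 | 0.0366 | 0.0211 | 0.0318 |
| 60 | 7 | 53 | 0.0239 | 0.0332 | 0.0203 | 0.0287 |

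Simulation with five ROIs at correlation 0.54 (40,000 null data sets per setting) agrees for nominal 0.02: 0.023 to 0.026 for REML and 0.025 to 0.037 for ML.

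**Family-wise error over the five ROIs.** In simulation, exact t-tests at 0.02 already give about 8%. The z reference with an unbiased variance gives about 9%, adding about 1.3 to 1.5 points.

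**Microbiome Aim 3, kcal, N=60.** Intercept, treatment, microbiome change and interaction make p=4, so df=56.

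- Unbiased variance: 2·P(t[56] > 1.960) = 5.5%
- Divisor-N variance: 1.960 × √(56/60) = 1.893, and 2·P(t[56] > 1.893) = 6.3%
- Simulation: 5.2% to 6.3% across model-based variants, and about 8% with the uncorrected sandwich

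**Microbiome Aim 3, abstinence, N=60.** The documents give no week-12 abstinence rate for the sub-study. At an assumed 20%, a model-based Wald test runs at about 4% and the uncorrected sandwich at about 8%. In a separate simulation without a small-sample correction, the level ran from 5.3% at an assumed 50% abstinence to 8.7% at 20%.

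**Neuroimaging Aim 2.** Section 6.8 states: "The hypothesis that cessation increases food intake will be tested at 0.05". Taking two conditions, three recall days (section 6.5.6) and a random intercept, the test has about 250 to 300 residual degrees of freedom. Simulation gives 0.049 to 0.053, which is essentially nominal.

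**The case against.** The strongest reply is that only z versus t follows from the text, and that costs about 0.4 percentage points at 0.02. This stands. A reader might infer that the 0.02 tests really run at 0.037. That needs ML, all five covariates and N=50 together; the plan does not state the first and only permits the second. A reader might also infer that the 5% tests run at 8%. For kcal that needs an uncorrected sandwich, which 6.12 does not specify, and the model-based logistic test is conservative. Section 6.9 does mention a subject-clustered jackknife variance, but only for microbiome Aim 1.

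A z-score is also named in neuroimaging Aim 2, but that test is within-subject and close to nominal. Neuroimaging Aim 3 and microbiome Aim 1 name no z-score.

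It can be argued that rounding 0.024 down to 0.02 absorbs the excess. The simulation does not support that, because the five-ROI family is already near 8% with exact tests. For the same reason, a t reference would not by itself deliver the promised 5%.

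Finally, microbiome Aim 3 is described as exploratory and its z-score is a rule for retaining terms. That is fair, and it lowers the weight of the point.

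What remains is that even the most favourable Aim 1 case exceeds its stated level, and that the plan leaves open the choices that decide how much larger the excess could be.

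**Conclusion.** The point holds in limited form and is minor. In neuroimaging Aim 1 the z reference makes a nominal 0.02 about 0.024 and a nominal 0.0167 about 0.020 to 0.021. Under ML the 0.02 becomes 0.026 to 0.027 without covariates, and at most 0.033 to 0.037 with all five. In microbiome Aim 3 the nominal 5% kcal interaction test runs at about 5.2% to 6.3% with a model-based variance and about 8% with an uncorrected sandwich. For abstinence the direction is not determined by the plan.

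These figures assume equal arms, normal errors, N of 50 to 60, and for abstinence the assumed rates shown. Neuroimaging Aim 2 (read as a random-intercept model), neuroimaging Aim 3 and microbiome Aim 1 are not affected. The choice of 0.02 for five ROIs is a separate issue and accounts for most of the gap from a 5% family error.

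**What to change.** In 6.11, Aim 1, replace the z-score with a REML fit and a t reference using Kenward-Roger or Satterthwaite degrees of freedom, and state which covariates enter the model.

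In 6.12, analyse the single week-12 kcal change by ordinary linear regression with t-tests. For abstinence, first settle the time points: 6.9 refers to week 12, while 6.5.6 names weeks 8 and 12 for this sub-study. If only week 12 is modelled, use logistic regression with likelihood-ratio or penalised-likelihood tests. If both weeks are modelled together, keep GEE with a small-sample-corrected sandwich and a t reference.

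The cost is a few sentences and a software option. The critical value at 0.02 rises from 2.33 to about 2.39 to 2.42, with a small loss of power. No procedure or sample size changes. The change removes only the z-related excess, about 1.3 to 1.5 points of family-wise error across the five ROIs.

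### Neuroimaging Aim 2 tests a cessation hypothesis with a pre/post contrast that has no smoking-status term, so the result cannot be read as an effect of cessation

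*Combined protocol and SAP*

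**What the plan says.** Section 6.8 states the Aim 2 hypothesis and its level: "The hypothesis that cessation increases food intake will be tested at 0.05", "with power for effect sizes $\sim d=0.32". The same section says the investigators "have chosen a completed sample ($N=60$) that will achieve at least 80% power using 2-sided tests".

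Section 6.11, Aim 2, takes average daily calories from the food recalls as the outcome. It describes the test thus: "The first comparison (pre vs. post-treatment) is within-subject, and will be analyzed using mixed models regression with subject specific random effects". The model is then specified: "we include a binary predictor for condition, a categorical indicator for serial day, and we will test using the z-score corresponding to condition". Candidate mediators are added by "entering variables as time-varying (condition varying) predictors, along with subject specific random effects" and are described as "BOLD signal change or subjective responses in cessation vs. smoking".

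Section 6.12 includes smoking rate as a covariate in microbiome Aim 1 "because not all participants will have maintained smoking abstinence from TQD through EOT". The parent weight analysis in section 6.10 also brings smoking status into the model.

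Sections 3.2 and 6.2.13 set no abstinence requirement for Scan 2. CO, past-24-hour smoking and timeline follow-back (TLFB) are collected at that visit. Section 2.2 frames neuroimaging Aim 2 as treatment-induced change, BAS+ versus SC.

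**The concern.** The hypothesis is about cessation, but the tested term separates visits before treatment from visits after it. A participant who never quit, or who relapsed, counts at the post time point exactly as an abstainer does. Two errors follow. A real effect of quitting on intake is averaged with whatever happens in continuing smokers. And anything else that differs between the two time points (elapsed time, the patch course, counselling, repeated dietary recall) enters the same coefficient and is reported as cessation.

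A null result could then not be read as showing that quitting leaves intake unchanged, nor a positive one as showing that quitting raises it. Aim 3 has a related gap. It speaks of a cessation condition and cessation-induced deficits, but regresses pre/post difference scores without a smoking term.

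**Working it through.** **1. Which term is tested.** Condition could in principle mean treatment arm, because the Aim 2 text says the predictor is included as before, and Aim 1 used a group indicator. But the comparison is within-subject and its predictors vary with condition over time. Arm does not vary within a subject, so condition is pre/post. If arm were meant, cessation would not be tested at all.

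**2. The plan's own figure.** Inputs from section 6.8: d=0.32, two-sided alpha 0.05, N=60. Section 3.2 gives N of about 50. For a paired t-test, the noncentrality is d√N.
- N=60: 0.32 × √60 = 2.48, power 68%.
- N=50: 0.32 × √50 = 2.26, power 60%.

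The stated figure of at least 80% does not reproduce on this reading. By the normal approximation it needs 77 participants, or, at N=60, a d on the raw-SD scale with a pre/post correlation of about 0.61. The scale of d is not defined, so this alone does not prove an error. It is not part of the present point; 68% is used below only as the reference.

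**3. Dilution.** Let q be the fraction abstinent at the post time point. The documents give no week 8 or week 12 rate, only 13% and 25% at 26 weeks (section 6.7), so q is an assumption shown over a range. Assume also that d=0.32 holds in quitters and that continuing smokers do not change. Then d_eff = q × 0.32.

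| q | d_eff | Power, N=60 | Power, N=50 |
|---|---|---|---|
| 0.25 | 0.080 | 9% | 9% |
| 0.35 | 0.112 | 14% | 12% |
| 0.45 | 0.144 | 20% | 17% |
| 0.60 | 0.192 | 31% | 27% |
| 1.00 | 0.320 | 68% | 60% |

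Mixing the two groups also adds a little variance: d_eff is divided by √(1 + q(1−q)d²), at most √(1 + 0.25 × 0.1024) = 1.013. This changes power by less than one percentage point.

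**4. A milder assumption.** If smokers show half the quitters' effect, d_eff = 0.32 × (q + 0.5(1−q)). That is 0.200 at q=0.25 and 0.232 at q=0.45, giving 33% and 42% power at N=60.

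**5. The opposite error.** Suppose cessation has no effect, but other causes shift intake by 0.2 SD of the within-subject change. The noncentrality is 0.2 × √60 = 1.55, and the condition term is significant 33% of the time at N=60 (28% at N=50).

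**6. Power of abstainers versus smokers.** Under the assumptions of step 3 with equal variances, a two-sample t-test on the changes has noncentrality 0.32 × √(N q(1−q)).
- q=0.25, N=60: 0.32 × √11.25 = 1.07, power 18%.
- q=0.45, N=60: 0.32 × √14.85 = 1.23, power 23%.
- q=0.60, N=60: 0.32 × √14.40 = 1.21, power 22%, below the 31% of the pre/post test.
- N=50: 16-20% over q=0.25 to 0.45.

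**The case against.** The strongest reply has four parts.

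*The path model names abstinence.* The later step in 6.11 describes the relation between abstinence and calories. That stands as far as it goes: a reader might infer that the mediation paths are mislabelled throughout, and the text does not establish this. But it never says how abstinence is coded, so the gap remains, and the first test is unaffected.

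*The size is assumed.* This stands. The week 8 rate is not in the documents, zero change in smokers is an extreme case, and section 6.8 does not say that d=0.32 refers to quitters. If it came from a mixed population, the dilution is already in it.

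*Bias can go either way.* This also stands. A reader might infer that the contrast measures time rather than cessation, or that it must understate the effect. Neither is supported: it contains the quitters' cessation effect along with the other changes, and BAS+ is itself expected to reduce intake in half the sample.

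*Abstinence is self-selected and the abstinent group is small.* Correct. Comparing abstainers with smokers is not a randomised comparison, and step 6 shows little or no gain in power. This limits the remedy but does not rescue the existing test.

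A reader might also point to the standardised cigarette before Scan 1. It cannot carry this point, because the tested outcome is calories from food recalls. Section 6.2.13 also collects recent smoking at both scans in order to control for exposure.

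**Conclusion.** The concern holds as a mismatch between hypothesis and test. Run as written, the Aim 2 pre/post term estimates average change over the treatment period in a mixed group of quitters and smokers, and cannot support a conclusion about cessation. That rests on the text alone. The microbiome sub-study and the parent weight analysis both bring smoking into their models; neuroimaging Aim 2 does not, and no reason is given.

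The numerical consequence is illustrative. The fall from 68% to 9-20% power at N=60 depends on an assumed 25-45% abstinent, on d=0.32 applying to quitters only, and on no change in smokers. At 60% abstinent it is 31%; with a half-sized response in smokers it is 33-42% over the 25-45% range. These figures show that dilution could be large, not that it will be. The 33% rate of significance from a 0.2 SD non-cessation shift likewise depends on the assumed size of the shift.

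**What to change.** In section 6.11, Aim 2, enter biochemically verified abstinence or TLFB smoking rate as a time-varying predictor alongside time and treatment arm, and test the cessation hypothesis on that term. Use the same variable, defined once, as abstinence in the path model. Call the plain pre/post contrast change over time, and call the abstinence contrast observational because abstinence is not randomised.

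In Aim 3 the difference-score regression has no condition term to replace, so add the change in smoking status or rate as a term.

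Reconcile the Aim 2 estimand across sections 2.2, 6.8 and 6.11: treatment-induced change under BAS+ versus SC, or the effect of cessation. If both are wanted, state each with its own test.

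The cost is analysis-plan wording; CO and TLFB are already collected. The downside is that the abstinent group is small, so intervals will be wide and power stays low (about 18-23% at N=60 for abstainers versus smokers with 25-45% abstinent). The gain is a correctly labelled estimand, not power.

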2.2 Neuroimaging Sub-Study

Aim 1: Identify putative brain mechanisms underlying BAS+ (vs. SC) treatment for smoking cessation and PCWG.

H1a: BAS+ (vs. SC) will decrease food cue-induced activity in insula, anterior cingulate cortex (ACC), orbitofrontal cortex (OFC), and ventral striatum/accumbens (VS/NAC);

H1b and H1c: (Hb) BAS+ (vs. SC) will decrease food reinforcement choice-related activity in VS/NAC and ventromedial prefrontal cortex (vmPFC); and **(H1c)** will produce corresponding decreases in food craving, reward, and reinforcement at the behavioral level (task performance).

Aim 2: To evaluate the relative contribution of treatment-induced changes in task related brain signal (Food Cue Response, Food Reinforcement/Choice) in prediction of post treatment food intake.

H2a: Brain network response (H1a-b) in the BAS+ (vs. SC) group will characterize treatment-induced changes in caloric intake (and quit success) more accurately than clinical (age, sex, nicotine dependence, BMI) and behavioral (withdrawal, craving, food reinforcement) measures alone.

H2b: The relative contribution of domain specific brain signal (food cue reactivity and food reward) to the prediction of treatment-induced change in caloric intake will be evaluated (regression model).

Aim 3: Test whether BAS+ (vs. SC) induced change in neural responses to food cues and food reinforcement is a stronger predictor of food intake among smokers with greater cognitive control.

We predict that the relationship of food cue and choice-related neural activity (e.g., VS/NAC BOLD signal; BAS+ vs. SC) will be a stronger predictor of caloric intake among smokers who also show greater working memory-related neural activity (i.e., DLPFC BOLD signal) at baseline and post treatment. Regions of interest for food cue and choice-related neural activity will be selected from those shown to be sensitive to cessation in Aim 1.

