3.2 General Design - Neuroimaging Sub-Study

We propose to study a sub-sample of consecutively recruited participants (N=~50) enrolled in the parent randomized clinical trial. As displayed in **Figure 2**, an equal number of fMRI eligible smokers from the BAS+ or SC treatment group will be studied before treatment (~week -2) and during the final week of nicotine patch therapy (~week 7-8). As part of the parent study, smoking will be assessed by self-report and biochemically confirmed weekly after quitting, at EOT (week 8), and at the 12 and 26 week follow-ups. Weight will be assessed at these same time points. Food intake will be measured by three consecutive days of 24-hour food recalls at baseline and 4-, 8-, 12- and 26-weeks post-TQD.

Scans identified in **Figure 2** and included within the Study Procedures Section represent approximations. Participants will complete scans as designated in Figure 2 and the Study Procedures, but will be permitted a degree of flexibility at the discretion of the Principal Investigator due to extenuating circumstances.

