4.3 Accrual - Neuroimaging Sub-Study

Eligible participants enrolled in the parent study who meet the fMRI eligibility criteria will have the opportunity to participate in the neuroimaging sub-study. We estimate that in order to achieve a sample of ~50 participants who complete the neuroimaging sub-study with usable data, we will need to enroll ~75 participants into the sub-study. Accrual estimates are based on our extensive experience conducting neuroimaging studies and specifically recruitment of fMRI subsamples from larger clinical trials. To ensure retention, we: (1) educate subjects about the benefits of participation and knowledge gained from the study; (2) schedule sessions at convenient times; (3) provide reminder calls; and (4) provide incentives for completion of sessions and assessments. This accrual rate is highly feasible based on our prior work.

CONFIDENTIAL

This material is the property of the University of Pennsylvania. Do not disclose or use except as authorized in writing by the study sponsor

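### Neuroimaging H2a and Aim 3 ask BAS+ versus SC questions, but the models and power given for them contain no treatment-arm term

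*Combined protocol and SAP*

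**What the plan says.** Objectives (section 2.2). H2a reads "Brain network response (H1a-b) in the BAS+ (vs. SC) group will characterize treatment-induced changes in caloric intake", more accurately than clinical and behavioural measures alone. Aim 3 is to "Test whether BAS+ (vs. SC) induced change in neural responses to food cues and food reinforcement is a stronger predictor of food intake" in participants whose cognitive control is higher. Sections 1.2 and 2.2 add that cognitive control will be tested as a moderator of the influence of BAS+ on food intake. H2b names no arm: it asks how much each brain signal contributes to predicting change in caloric intake.

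Analysis (section 6.11). Aim 1 has an explicit binary indicator for BAS+ versus SC. Aim 2 begins with a within-subject pre/post comparison, tests a predictor called *condition*, and enters candidate mediators that vary by condition. Its path model runs from abstinence to food intake, with intervening variables described as "BOLD signal change or subjective responses in cessation vs. smoking". Aim 3 is retitled around working-memory deficits induced by cessation, and its interaction is given as "cessation condition by food reinforcement by working memory on food intake". It is then simplified to a linear regression of pre/post food-intake differences on the BOLD difference and a candidate moderator.

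Power (section 6.8). The authors "have chosen a completed sample ($N=60$) that will achieve at least 80% power using 2-sided tests". Aim 2 is powered on cessation increasing food intake. Aim 3 is powered as a two-way, one-sample interaction of d=0.36 with 80% power at a corrected alpha of 0.02. Section 3.2, in contrast, says "We propose to study a sub-sample of consecutively recruited participants (N=~50"), and section 4.3 says that to obtain about 50 with usable data "we will need to enroll ~75 participants into the sub-study". On allocation, section 3.2 states that "an equal number of fMRI eligible smokers from the BAS+ or SC treatment group will be studied".

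**The concern.** A question about BAS+ versus SC needs arm in the model, either as the start of a mediation path or in an interaction. Neither aim lists it. A pre/post or cessation contrast pools the two arms, all of whose members attempt to quit with nicotine patch and counselling. A significant pooled coefficient says that brain change and food-intake change go together, or do so more strongly at some level of working memory. It does not say that BAS+ caused the change or that the relation differs by arm.

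What is at stake is the sub-study's stated purpose of explaining why BAS+ may work and for whom. A pooled finding could be reported as a BAS+ mechanism, and a real arm difference could go unseen. The plan does state an arm interaction where one is wanted elsewhere: Aim 3 of the microbiome sub-study (section 6.12) enters treatment by microbiome change.

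**Working it through.** **Inputs.** Two-sided tests, N=60 completed, Aim 3 alpha 0.02, d=0.36 with 80% power (section 6.8). About 50 completers and equal arms (section 3.2). About 75 enrolled (section 4.3). Normal quantiles: 2.326 (alpha 0.02), 1.960 (alpha 0.05), 0.842 (80% power).

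**The plan's own figure.** For a one-sample standardized coefficient, power = Φ(d√N − z) and the detectable value is (z + 0.842)/√N.
- N=60, alpha 0.02: 0.36 × 7.746 − 2.326 = 0.462, so power is 68%, not 80%. Detectable value: 3.168/7.746 = 0.41.
- N=60, alpha 0.05: 0.36 × 7.746 − 1.960 = 0.829, so power is 80%. Detectable value: 2.802/7.746 = 0.36.

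The stated 0.36 at N=60 therefore matches the uncorrected alpha of 0.05, not the stated 0.02.

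**Do the stated powers contain an arm comparison?** Each is recomputed as a one-sample test and as a comparison of two equal arms:

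| Item in section 6.8 | Stated | One-sample, N=60 | One-sample, N=75 | Two arms, N=60 | Two arms, N=75 |
|---|---|---|---|---|---|
| Aim 2, d=0.32, alpha 0.05 | at least 80% | 69.8% | 79.1% | 23.6% | 28.3% |
| Aim 2b, d=0.5, alpha 0.01 | 96% | 90.3% | 96.0% | 26.1% | 34.1% |
| Aim 3, d=0.36, alpha 0.02 | 80% | 67.8% | 78.6% | 17.6% | 22.1% |
| Aim 3, d=0.35, alpha 0.02 | 77% | 65.0% | 76.0% | 16.6% | 20.9% |
| Aim 3, d=0.55, alpha 0.02 | 98% | 97.3% | 99.3% | 42.2% | 52.2% |

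All five come within two points as one-sample tests at N=75, and none does as a two-arm test. The documents do not say that 75 was used. The table shows only that the power figures, like the models, carry no arm contrast.

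**Size of an arm contrast.** With N/2 per arm, the difference between two standardized coefficients has standard error √(4/N), so the detectable difference is (z + 0.842)√(4/N).
- N=60, alpha 0.02: 3.168 × 0.2582 = 0.82.
- N=50, alpha 0.02: 3.168 × 0.2828 = 0.90.
- Power if the arm difference were 0.36: Φ(0.36/0.2582 − 2.326) = Φ(−0.93) = 18% at N=60, and Φ(0.36/0.2828 − 2.326) = Φ(−1.05) = 15% at N=50.

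**What the pooled test responds to.** A simulation used 3,000 data sets per case, N=60 with 30 per arm, independent standard normal BOLD change and working memory, residual SD 1, and alpha 0.02. It compared the model as written with one adding arm and all its interactions.
- Coefficient 0.36 in both arms (no arm difference): the pooled model rejects 57%, the arm interaction 2%.
- Coefficients +0.36 and −0.36: the pooled model rejects 6%, the arm interaction 48%.
- Coefficient 0.82 in BAS+ and 0 in SC: the arm interaction rejects 59%, not the nominal 80%. The closed-form figures above are therefore optimistic.

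**The case against.** Four points can be made for the plan.

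First, Aim 2 introduces its condition predictor as following what went before, and the only earlier binary predictor is Aim 1's group indicator. Condition might thus mean arm. That does not hold. The comparison is called within-subject and the predictors vary by condition, whereas randomised arm is fixed for each person. The contrast is also named as cessation against smoking.

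Second, Aim 3 is confined to regions found sensitive to treatment in Aim 1, which does have an arm term. This links arm to BOLD change for the chosen regions. It does not test whether that change carries an arm effect to food intake, or whether the relation differs by arm.

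Third, H2b needs no arm term, and the working-memory interaction does test the pooled part of Aim 3. This stands.

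Fourth, a reader might infer that Aims 2 and 3 are wholly untested, or that condition is no more than time. The documents do not support either. H2b and the pooled moderation can be addressed as written. The path model starts from abstinence, which differs between participants: section 6.7 expects 13% and 25% abstinent at six months.

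**Conclusion.** The point holds for H2a, for the arm part of Aim 3, and for the promised test of cognitive control as a moderator of BAS+. No arm term is listed in the models or the power for these, so following the plan would leave the BAS+ versus SC contrast unanswered.

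At the stated two-sided alpha of 0.02, the one-sample detectable coefficient at N=60 is 0.41, and the detectable arm difference is about twice that: 0.82, or 0.90 at N=50. These are differences in a standardized regression coefficient, not mean differences in SD units. They assume equal arms, unit residual variance and a normal approximation. The 18% and 15% powers further assume an arm difference of 0.36. The documents give no value for that difference; 0.36 is borrowed from the one-sample figure for scale.

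This is a mechanistic sub-study, and the parent trial's primary outcomes are not affected. It should be settled before the sub-study is analysed.

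**What to change.** Choose one of two routes and make sections 1.2, 2.2, 6.8 and 6.11 agree.

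- **Keep the arm questions.** In Aim 2, add arm, the path from arm through BOLD change to change in kcal, and an arm by BOLD change term. In Aim 3, add arm and its interaction with BOLD change by working memory, labelled exploratory. H2a's comparison of accuracy with clinical and behavioural measures also needs its own stated test, because an arm term alone does not provide one.
- **Drop the arm questions.** Reword H2a, Aim 3 and the cognitive-control statement as pooled pre/post questions, and make no claim about a BAS+ mechanism from them.

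Either way, restate power at the alpha actually used and at one agreed completed sample size: 0.41 at N=60 for the pooled coefficient, and about 0.82 (N=60) or 0.90 (N=50) for an arm difference. No new data, visits or participants are needed. The cost is rewording and less favourable power figures, with the three-way term openly underpowered for modest effects.
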